9.8.2 Rash

Individuals who develop a generalized rash will be monitored closely. Study drug dosing should be interrupted if a subject develops a generalized rash of Grade 3 or higher (Section 13.1.1.4), or a rash that is considered a serious adverse event (SAE). The investigator will notify the medical monitor of any rash that results in interruption of study drug, is Grade 3 or higher, or is an SAE. Investigators should consider additional evaluation including laboratory testing (e.g., complete blood count with differential, liver function tests), photographs of the rash, and dermatology consultation. The investigator may consider resumption of study drug if considered clinically appropriate.

9.9 Removal of Subjects

Subjects may withdraw from the study at any time at their own request or the request of the subject's parent or legal guardian. Subjects may be withdrawn at any time at the discretion of the investigator or Vertex for safety, behavior, noncompliance (study drug dosing or study

procedures), or administrative reasons. A subject who withdraws from study drug treatment will continue to be followed unless the subject withdraws consent.

In addition, a subject must be discontinued from study drug treatment if the subject meets any of the following criteria:

- Meets any of the stopping (discontinuation) criteria (Section 9.8)
- Becomes pregnant (Section 11.4.7.2)

If a subject does not return for a scheduled visit, reasonable effort will be made to contact the subject. In any circumstance, reasonable effort will be made to document subject outcome. The investigator will inquire about the reason for withdrawal, request that the subject return all unused investigational product(s), request that the subject return for a Safety Follow-up Visit, if applicable (see Section 9.1.3), and follow up with the subject regarding any unresolved AEs.

If a subject withdraws consent for the study, no further assessments will be performed. Vertex may retain and continue using the study data and samples after the study ends, and may use the samples and information in the development of the study compound, for other drugs and diagnostics, in publications and presentations, and for education purposes. If a subject withdraws from the study, the study data and samples collected will remain part of the study. A subject will not be able to request the withdrawal of his/her information from the study data. A subject may request destruction of the samples collected from him/her during the study as long as those samples can be identified as his/her samples.

9.10 Replacement of Subjects

Subjects who withdraw or are withdrawn during the study drug Treatment Period will not be replaced.

10 STUDY DRUG INFORMATION AND MANAGEMENT

10.1 Preparation and Dispensing

Study drug may be dispensed only under the supervision of the investigator or an authorized designee and only for administration to the study subjects. An interactive web response system (IWRS) will be used to dispense dosage based on subject weight and age.

10.2 Packaging and Labeling

Study drug tablets will be supplied in blister cards by Vertex. Study drug labeling will be in compliance with applicable local and national regulations. Additional details regarding packaging, labeling, and dispensing for study drug will be in the Pharmacy Manual.

10.3 Study Drug Supply, Storage, and Handling

Table 10-1 provides the study drug information. The investigator, or an authorized designee (e.g., a licensed pharmacist), will ensure that all investigational product is stored in a secured area, under recommended storage conditions, and in accordance with applicable regulatory requirements. To ensure adequate records, all study drugs will be accounted for via the drug accountability forms as instructed by Vertex.

Detailed instructions regarding the storage, handling, and dispensation of the study drug will be provided in the Pharmacy Manual.

Table 10-1 Study Drug: Dosing Form/Route/Strength

Drug Name, Dosing Form, Route	Tablet Strength	
	Subjects 6 to <12 years and <30 kg	Subjects 6 to <12 years and ≥30 kg or ≥12 years
ELX/TEZ/IVA, FDC tablet, oral		
ELX	50 mg	100 mg
TEZ	25 mg	50 mg
IVA	37.5 mg	75 mg
IVA, tablet, oral	75 mg	150 mg

ELX: elexacaftor; FDC: fixed-dose combination; IVA: ivacaftor; TEZ: tezacaftor

Note: See Table 9-3 for details on study drug administration.

10.4 Drug Accountability

The pharmacist or designated study site staff will maintain information about the dates and amounts of (1) study drug received; (2) study drug dispensed to the subjects; and (3) study drug returned by the subjects. Subjects will be instructed to return all used and unused materials associated with the study drug to the site. These materials will be retained at the site according to instructions provided by Vertex or its designee. The study monitor will review study drug records and inventory throughout the study. If a site uses a site-specific drug accountability system and/or process, including processes associated with the destruction of returned materials, the process must be documented and approved by Vertex. The study monitor must review the drug accountability documentation on a regular basis. The study monitor will promptly communicate to Vertex any discrepancies he or she is unable to resolve with the site.

10.5 Disposal, Return, or Retention of Unused Drug

The study site staff or pharmacy personnel will retain all materials returned by the subjects until the study monitor has performed drug accountability. The investigator will ensure that the materials are destroyed in compliance with applicable environmental regulations, institutional policy, and any special instructions provided by Vertex. Destruction will be adequately documented.

The principal investigator, study site staff, including pharmacy personnel will assist Vertex with any recall activities (as applicable) and place impacted investigational medicinal product (IMP) in quarantine when requested.

10.6 Compliance

To ensure treatment compliance, the investigator or designee will supervise all study drug dosing that occurs at the site. At each visit, site personnel will review that the subject is compliant with study drug dosing and remind the subject of study drug dosing requirements. Compliance will also be assessed by ongoing study drug count.

If a subject demonstrates continued noncompliance of study drug dosing despite educational efforts, the investigator should consider discontinuing the subject from the study.

10.7 Blinding and Unblinding

This is an open-label study; however, subjects and their legally appointed and authorized representative (e.g., parent or legal guardian) should not be informed of their study-related SwCl,

LCI, and spirometry results until the study has been completed, regardless if the subject permanently discontinues treatment. In addition, the Vertex study team will not have access to the SwCl, LCI, or spirometry of the present study until the data lock of the parent study.

11 ASSESSMENTS

The schedule of assessments is shown in Table 3-1.

The following assessments must be performed in the order specified below when more than 1 assessment is required at a particular time point:

1. The CFQ-R should be completed before the start of any other assessments (except signing of ICF or assent) scheduled at that visit.
2. The MBW assessment should be performed before spirometry.

11.1 Subject and Disease Characteristics

Subject and disease characteristics include the following: demographics, medical history, height, and weight. Select demographic and medical history will be derived from the parent study.

11.2 Efficacy and Pharmacodynamics

11.2.1 Sweat Chloride

The sweat chloride test is a standard diagnostic tool for CF, serving as a biomarker of CFTR activity. Sweat samples will be sent to a central laboratory for testing and interpretation of results. Individual sweat chloride test results will not be disclosed to the study sites. Specific instructions for collection, handling, processing, and shipping of sweat chloride samples to the central laboratory will be provided separately. The sweat chloride test must be conducted predose relative to the morning dose of study drug during the Treatment Period. At each time point, 2 samples will be collected, 1 sample from each arm (left and right).

See Section 10.7 for information about access to SwCl results.

11.2.2 Multiple-breath Washout

The N₂-MBW testing will be performed in multiple replicates for each visit and the final LCI value will be calculated from the technically acceptable washout replicates by a central reader. The final LCI value at each visit will be the value provided by the LCI vendor based on the replicates.

At all visits, all MBW tests should be performed pre-bronchodilator as described in Section 11.2.3. The MBW should be performed before the spirometry assessment (Section 11). See Section 10.7 for information about access to LCI results.

11.2.3 Spirometry

Spirometry will be performed according to the American Thoracic Society Guidelines/European Respiratory Society Guidelines¹² and according to the additional guidelines that follow.

Pre-bronchodilator spirometry is defined as spirometry testing performed for subjects who have

- withheld their short-acting bronchodilators (e.g., albuterol) or anticholinergic (e.g., ipratropium bromide [Atrovent[®]]) for more than 4 hours before the spirometry assessment;

- withheld their long-acting bronchodilator (e.g., salmeterol) for more than 12 hours before the spirometry assessment; and
- withheld their once-daily, long-acting bronchodilator (e.g., tiotropium bromide [Spiriva®]) for more than 24 hours before the spirometry assessment.

At all visits, all spirometry assessments should be performed pre-bronchodilator. During the Treatment Period, spirometry assessments must be performed before study drug dosing (Section 9.6.1) at approximately the same time at each visit. In the event that a subject forgets to withhold bronchodilator(s), spirometry should be performed according to the following:

- If a subject's Day 1 spirometry assessment is pre-bronchodilator, but, on a subsequent visit, the subject forgets to withhold bronchodilator use, a post-bronchodilator spirometry assessment will be obtained for that visit only, and the visit will not be rescheduled.
- If, on Day 1, the subject forgets to withhold his/her dose of bronchodilator, spirometry should be performed post-bronchodilator, and all subsequent spirometric measurements (according to the schedule of assessments) should be performed post-bronchodilator.
- Each spirometry assessment will be recorded in the source documents as pre- or post-bronchodilator.

All sites will be provided with spirometers to be used for all study assessments. Spirometry data will be transmitted to a centralized spirometry service for quality review.

See Section 10.7 for information about access to spirometry results.

The measured spirometric values listed below will be converted to percent predicted values using the standard equations of the Global Lung Function Initiative (GLI).¹³

- FEV₁ (L)
- Forced vital capacity (FVC) (L)
- FEV₁/FVC (ratio)
- Forced expiratory flow, midexpiratory phase (FEF_{25%-75%}) (L/s)

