^d The Day 1 Visit should be on the same day as the last scheduled visit of the parent study (Section 9.1.1). Subjects whose Day 1 Visit is NOT within 1 day of the last scheduled visit of the parent study will repeat all Day 1 assessments. Subjects whose Day 1 Visit is within 1 day of the last scheduled visit of the parent study will NOT have to repeat any Day 1 assessments that were specified to be performed at the last scheduled visit in the parent study.

Table 3-1 Study VX20-445-119: Treatment Period and Safety Follow-up Visit									
Event/ Assessment ^a	Treatment Period					ETT Visit ^b	Safety Follow-up Visit (28 ± 7 Days After Last Dose of Study Drug ^c)	Comments	
	Day 1 ^d	Weeks 4, 8, 16, 24 (± 5 Days)	Weeks 12, 20, 28, 32, 40, 44, 52, 56, 64, 68, 76, 80, 88, 92 (± 5 Days)	Weeks 36, 48, 60, 72, 84 (± 5 Days)	Week 96 (± 10 Days)				
Standard 12-lead ECG	X	Weeks 8, 16, 24		Weeks 48, 72	X	X	X	Performed prior to any procedure that may affect heart rate (e.g., blood draws) and after subject has been at rest for at least 5 minutes (Section 11.4.5).	
Sweat chloride	X	X		Weeks 48, 72	X	X		Section 11.2.1	
Multiple-breath washout	X	X		Weeks 48, 72	X	X		Performed in multiple replicates, pre-bronchodilator, before the AM dose, and before spirometry assessment (Section 11.2.1).	
Spirometry	X	X		X	X	X	X	Performed pre-bronchodilator, before the AM dose, and at approximately the same time at each visit (Section 11.2.3).	
Pregnancy test	Urine	Serum	Urine	Serum	Serum	Serum	Serum	For all female subjects at telephone contacts, a urine pregnancy test will be performed with a home kit provided by the study site. Results of the home pregnancy test will be reported to the site by telephone (Section 11.4.2).	
Serum chemistry	X	X		X	X	X	X	Section 11.4.2	
Hematology	X	X		X	X	X	X		
Coagulation	X	Week 24		Weeks 48, 72	X	X			
Urinalysis	X			Week 48	X	X			
AEs and SAEs	Continuous from signing of the ICF through completion of study participation								Section 13.1; Completion of study participation is defined in Section 9.1.5.

Table 3-1 Study VX20-445-119: Treatment Period and Safety Follow-up Visit								
Event/ Assessment ^a	Treatment Period					ETT Visit ^b	Safety Follow-up Visit (28 ± 7 Days After Last Dose of Study Drug ^c)	Comments
	Day 1 ^d	Weeks 4, 8, 16, 24 (± 5 Days)	Weeks 12, 20, 28, 32, 40, 44, 52, 56, 64, 68, 76, 80, 88, 92 (± 5 Days)	Weeks 36, 48, 60, 72, 84 (± 5 Days)	Week 96 (± 10 Days)			

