12.3.1 General Considerations

Continuous variables will be summarized using the following descriptive summary statistics: the number of subjects (n), mean, SD, median, minimum value (min), and maximum value (max).

Categorical variables will be summarized using counts and percentages.

The **baseline value**, unless otherwise specified, for the long-term safety analysis will be the most recent non-missing measurement (scheduled or unscheduled) collected before the first dose of ELX/TEZ/IVA either in the parent study or the open label study, as applicable. The baseline value for the long-term efficacy analysis will be defined as the most recent non-missing measurement (scheduled or unscheduled) collected before the first dose of study drug in the parent study. For assessments collected in duplicate or triplicate, the baseline will be defined as the average of non-missing values.

Change (absolute change) from baseline will be calculated as Post-baseline value – Baseline value.

The **Efficacy Analysis Period** in the open-label study will include the time from the first dose of study drug in the open-label study to the last scheduled efficacy visit in the open-label study, unless otherwise specified.

The **Treatment-emergent (TE) Period** in the open-label study will include the time from the first dose of study drug in the open-label study to 28 days after the last dose of the study drug in the open-label study or to the completion date of study participation (as defined in Section 9.1.5), whichever occurs first.

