8.3.2.2 Analysis Method

Absolute change in SwCl from baseline:

The mixed-effects model for repeated measures (MMRM) for the parent study 116-FAS will be same as that described in the SAP for Study 116. In the MMRM for the OL-FAS, the absolute change from baseline in SwCl will be the dependent variable. The model will include treatment group (as randomized in the parent study), visit, and treatment-by-visit interaction as fixed effects, with continuous baseline LCI_{2.5} from the parent study and weight at Screening (<30 versus ≥30 kg) of the parent study as covariates.

The repeated-measures analysis will be based on the restricted maximum likelihood method assuming an unstructured covariance structure to model the within-subject errors. The denominator degrees of freedom will be based on the method proposed by Kenward-Roger⁶. If the model fails to converge due to the unstructured covariance assumption, a compound symmetry covariance structure will be used to model the within-subject errors. In the MMRM approach, assuming that the data are missing at random, no imputation of missing data will be performed.

Results from the 2 MMRMs (for the parent study and for the OE) will be presented in a single summary table. The number of subjects, least-squares means (LS means) for absolute change from baseline at scheduled visits within each treatment group (as randomized in the parent study) along with the corresponding standard error (SE), and 95% confidence interval (CI) will be presented. The LS means (±SE) for absolute change from baseline at each visit will also be plotted by treatment group (as randomized in the parent study).

In addition, the descriptive statistics for raw values and absolute changes from baseline by treatment group (as randomized in the parent study) and OL visit will be presented for the OL-FAS.

Absolute change in LCI_{2.5} from baseline:

Analysis of this endpoint will be based on an MMRM similar to the analysis of the absolute change from baseline in SwCl. A descriptive summary of raw values and absolute changes from baseline will also be presented.

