8.3.3.2 Analysis Method

Absolute change in ppFEV₁ from baseline:

Analysis of this endpoint will be based on an MMRM similar to the analysis of the absolute change in SwCl. A descriptive summary of raw values and absolute changes from parent study baseline will also be presented.

The primary analysis will use the spirometry data obtained at clinic only. An additional analysis may be performed to include all available spirometry data obtained at clinic and obtained at home, if the spirometry data obtained at home are assessed to be reasonably consistent with the spirometry data obtained at clinic.

Absolute change in CFQ-R respiratory domain (RD) score from baseline:

Analysis of this endpoint will be based on an MMRM similar to the analysis of the absolute change in SwCl. A descriptive summary of raw values and absolute changes from parent study baseline will also be presented. In addition, the descriptive summary for raw values and the absolute change from parent study baseline of the parent version's CFQ-R RD score will be presented.

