11 LIST OF APPENDICES

Appendix A: Analysis Visit Windows for Safety and Efficacy Assessment

Table 11-1 Analysis Visit Windows for Safety and Efficacy Assessments

Assessment	Visit ¹	Target Study Day	Analysis Visit Window ^{2,3,4} (in study days)
Spirometry Weight, Height and BMI as well as the corresponding z-score	Parent Study Baseline	--	≤1 corresponding to the first dose date of parent study
	OL Week 4	29	(1, 43]
	OL Week 8	57	(43, 85]
	OL Week 16	113	(85, 141]
	OL Week 24	169	(141, 211]
	OL Week 36	253	(211, 295]
	OL Week 48	337	(295, 379]
	OL Week 60	421	(379, 463]
	OL Week 72	505	(463, 547]
	OL Week 84	589	(547, 631]
	OL Week 96	673	(631, 729]
	OL Safety Follow-up	Not applicable	Use nominal visit
Sweat Chloride, LCI _{2.5} , CFQ-R	Parent Study Baseline	--	≤1 corresponding to the first dose date of parent study
	OL Week 4	29	(1, 43]
	OL Week 8	57	(43, 85]
	OL Week 16	113	(85, 141]
	OL Week 24	169	(141, 253]
	OL Week 48	337	(253, 421]
	OL Week 72	505	(421, 589]
	OL Week 96	673	(589, 729]
Hematology Serum Chemistry Pulse Oximetry Vital Signs (excluding Weight, Height and BMI as well as the corresponding z-score)	TC Safety Baseline	1	Defined in Section 8.1
	OL Week 4	29	[1, 43] where day 1 is post-dose measurement
	OL Week 8	57	(43, 85]
	OL Week 16	113	(85, 141]
	OL Week 24	169	(141, 211]
	OL Week 36	253	(211, 295]
	OL Week 48	337	(295, 379]
	OL Week 60	421	(379, 463]
	OL Week 72	505	(463, 547]
	OL Week 84	589	(547, 631]
	OL Week 96	673	(631, 687]
	OL Safety Follow-up ⁴	Not applicable	Use nominal visit
Standard 12-lead ECG	TC Safety Baseline	1	Defined in Section 8.1
	OL Week 8	57	[1, 85] where day 1 is post-dose measurement
	OL Week 16	113	(85, 141]
	OL Week 24	169	(141, 253]
	OL Week 48	337	(253, 421]
	OL Week 72	505	(421, 589]
	OL Week 96	673	(589, 687]
		OL Safety Follow-up ⁴	Not applicable

Table 11-1 Analysis Visit Windows for Safety and Efficacy Assessments

Assessment	Visit ¹	Target Study Day	Analysis Visit Window ^{2,3,4} (in study days)
Coagulation	TC Safety Baseline	1	Defined in Section 8.1
	OL Week 24	169	[1, 253] where day 1 is post-dose measurement
	OL Week 48	337	(253, 421]
	OL Week 72	505	(421, 589]
	OL Week 96	673	(589, 687]

Notes:

¹Visit name for analysis purpose is used to report data in tables and figures.

²The analysis visit windows will be applied using the following rules for both scheduled and unscheduled visits:

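### Low priority: the extension's Day 1 fixes the bronchodilator state of all later spirometry, but ppFEV1 change is measured from the parent-study baseline, and the SAP never uses pre/post status

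*Protocol*

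**What the plan says.** **Bronchodilator state.** Protocol 11.2.3 asks for pre-bronchodilator spirometry throughout and treats lapses in two ways. If Day 1 was pre-bronchodilator, a later lapse affects only the visit at which it happens. If the lapse is on Day 1, "all subsequent spirometric measurements (according to the schedule of assessments) should be performed post-bronchodilator". Day 1 here is Day 1 of the extension, to which Protocol section 3 ties all visits. The status of each test goes into the source documents.

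**Baseline.** Protocol 12.3.1 defines the efficacy baseline as the most recent non-missing value "collected before the first dose of study drug in the parent study". SAP 8.1 says the same. SAP 8.3.3.2 applies it to ppFEV1, and the spirometry rows of SAP Appendix A give the baseline window as "≤1 corresponding to the first dose date of parent study".

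**Multiple-breath washout (MBW).** Table 3-1 describes MBW as "Performed in multiple replicates, pre-bronchodilator, before the AM dose, and before spirometry assessment". Protocol 11.2.2 adds: "At all visits, all MBW tests should be performed pre-bronchodilator as described in Section 11.2.3". The spirometry row of Table 3-1 also specifies pre-bronchodilator testing and shows no exception for a Day 1 lapse.

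**Analysis.** The rule in SAP 8.3.3.2 on which spirometry enters the ppFEV1 analysis concerns where the test was done: "The primary analysis will use the spirometry data obtained at clinic only". Appendix A selects values by distance from the target day. The spirometry handling rules in Appendix C cover age, height and race.

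**The concern.** A rule that fixes the test condition by its state on one day protects within-subject change only if that day supplies the baseline. Here it does not. Extension Day 1 is neither the efficacy baseline nor inside any extension spirometry window, since the first window opens after Day 1. The rule therefore aligns later tests with a value that the extension's ppFEV1 change does not use.

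Whenever the Day 1 state differs from the parent-baseline state, the acute bronchodilator response enters the long-term change. With a pre-bronchodilator parent baseline and a Day 1 lapse, it is added at every later post-bronchodilator visit, always in the same direction. With a post-bronchodilator parent baseline and a pre-bronchodilator Day 1, it is subtracted. The missing-at-random assumption in SAP 8.3.2.2 does not help, because these values are observed but not comparable with baseline.

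A Day 1 lapse may also reach the parent-study results. A subject whose Day 1 is within one day of the last parent visit "will NOT have to repeat any Day 1 assessments that were specified to be performed at the last scheduled visit in the parent study", so the same test may serve both studies. For sweat chloride, "Results from the 2 MMRMs (for the parent study and for the OE) will be presented in a single summary table", and the ppFEV1 analysis is to be similar. Whether such a test enters the parent model depends on the Study 116 SAP, which is not among the documents.

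**Working it through.** The plan states no figure on this point to reproduce. The check is a visit count, followed by an illustrative size.

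**1. Visits (Table 3-1; the lists agree with SAP Appendix A)**
- Spirometry after Day 1 in the treatment period: Weeks 4, 8, 16, 24, 36, 48, 60, 72, 84, 96 = 10.
- MBW after Day 1 in the treatment period: Weeks 4, 8, 16, 24, 48, 72, 96 = 7.
- Spirometry without MBW: Weeks 36, 60, 84 = 10 − 7 = 3.

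Early-termination and safety follow-up tests are not counted. A subject who stops early has fewer visits.

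**2. Mismatched visits per Day 1 lapse, if the parent baseline was pre-bronchodilator**
- Protocol 11.2.3 followed as written: 10 of 10.
- If sites instead test pre-bronchodilator at all 7 visits shared with MBW: 3 of 10. This departs from the written Day 1 rule and leaves one subject with 7 pre- and 3 post-bronchodilator values.

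**3. Are the MBW rule and the Day 1 rule compatible?** MBW must come first and be pre-bronchodilator. Under the Day 1 rule, spirometry follows and must be post-bronchodilator. Both are met if the bronchodilator is withheld for MBW and taken between the two tests. So the texts can be satisfied together, but no passage states that sequence, and the spirometry row of Table 3-1 does not allow for it.

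**4. Size at a mismatched visit**

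Shift in group mean ≈ k × d / n, where k is the number of lapsing subjects, d the acute response in ppFEV1 points and n the group size. This treats all n subjects as observed at the visit.

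Assumptions not in the documents: d = 3 to 8, and an even split of the roughly 108 expected subjects (Protocol 12.1), so n = 54 per parent-study group, with all lapses in one group.

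| k | n = 54 (one group) | n = 108 (all subjects) |
|---|---|---|
| 1 | 3/54 = 0.06 to 8/54 = 0.15 | 3/108 = 0.03 to 8/108 = 0.07 |
| 5 | 15/54 = 0.28 to 40/54 = 0.74 | 15/108 = 0.14 to 40/108 = 0.37 |

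Lapses needed to move one group's mean by 1 point: 54/8 = 6.75, so 7, up to 54/3 = 18.

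**5. Values left out of a sensitivity analysis**

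Scheduled values: 108 × 10 = 1,080. One affected subject: up to 10 (10/1,080 = 0.93%). Five: up to 50 (50/1,080 = 4.6%).

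**The case against.** The strongest reply is that the harm depends on things the documents do not show: the bronchodilator state at the parent baseline, the parent study's own lapse rule, how the Study 116 SAP treats pre/post status, and how often subjects lapse. Pre-bronchodilator testing is the default at every visit, ppFEV1 sits below the secondary endpoints, the primary objective is safety, and 7 to 18 of 54 subjects would have to lapse to move a group mean by 1 point. All of this stands. It sets the priority low, but it does not change the fact that the rule is anchored to the wrong day, or that the analysis has no means of noticing.

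Three stronger readings are tempting and are not supported:

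- **That the MBW rule and the Day 1 rule contradict each other.** They do not strictly, as step 3 of the working shows. What is missing is a stated sequence.
- **That the plan itself yields anywhere from 3 to 10 mismatched visits.** As written it yields 10. A lower count arises only if sites test pre-bronchodilator at shared visits, against the Day 1 rule.
- **That anchoring to the parent baseline removes every mismatch.** If sites let the MBW rule decide the state at the 7 shared visits, a subject with a post-bronchodilator parent baseline is mismatched there under either anchor. Re-anchoring is complete only once the MBW passages are reconciled.

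A further fair point is that SAP 9.2 implies the study was already under way. Changing the rule for subjects already switched to post-bronchodilator testing would split their series, so the fix has to exempt them.

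**Conclusion.** The concern holds at low priority. The Day 1 rule is tied to a visit that is not the ppFEV1 baseline, and nothing in the SAP uses pre/post status. If the parent baseline was pre-bronchodilator, a Day 1 lapse followed as written mismatches all 10 later treatment-period spirometry visits for a subject who attends them all.

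The likely effect on a group mean at a mismatched visit is about 0.06 to 0.15 points per lapsing subject. That rests on an assumed response of 3 to 8 points and an assumed 54 subjects per group; the number of lapses is unknown. A reader might infer that the long-term ppFEV1 result is materially biased. The documents give no lapse rate to support that, and the illustrative figures point the other way. No hypothesis test depends on ppFEV1, and LCI2.5 is unaffected provided MBW is done pre-bronchodilator as required.

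**What to change.** 1. **Protocol 11.2.3.** For subjects not already switched, tie the bronchodilator state of spirometry to that of the parent-study baseline, and let a Day 1 lapse that departs from it affect Day 1 alone. Both parts are needed: limiting the lapse to Day 1 without re-anchoring would mismatch a subject whose parent baseline was post-bronchodilator. Identify subjects already switched and handle them in the analysis; do not switch them back.
2. **Protocol 11.2.2, 11.2.3 and Table 3-1.** Reconcile these passages so that the order and condition of MBW and spirometry at the 7 shared visits are explicit, and so that the spirometry row agrees with the lapse rule.
3. **SAP 8.3.3.2, before database lock.** Confirm that pre/post status is in the analysis data, and add it if not. Add one ppFEV1 sensitivity analysis that leaves out values whose status differs from the parent baseline, run only if such values exist. Leave the main analysis unchanged.

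**Cost.** A short amendment, a data check, possibly one added field, and one extra analysis in a SAP that plans no sensitivity analysis even for the secondary endpoints (8.3.2.3). The eCRF and the central spirometry transfer are not among the documents, so status may already be captured. The sensitivity analysis would leave out up to 10 of about 1,080 scheduled values per affected subject; the main analysis loses none. If an amendment is not practical, item 3 can stand alone.
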